## 8. Proposed outcome measures:

**8.1 Primary Endpoint (outcome)** Primary analysis will be the comparison of the proportion of participants in active versus control groups who pass a peanut challenge test at the end of six months.

## 8.2 Secondary Endpoints

- -
- The proportion of participants from the control group who pass a peanut challenge after receiving the active intervention
- The fold increase and absolute increase in threshold (amount of peanut protein tolerated) for the active and control group members after intervention.
- Quality of life scores in active treatment group after intervention and in control group after waiting list control
- Quality of life scores before and after intervention for both active and control groups (disease-specific validated tool
- Immunological outcomes: results of cellular and humoral assessments of immune response related to the development of allergy or tolerance to peanut
- Safety outcomes; incidence and nature of adverse events
- Recruitment source: assessment of compliance and efficacy in groups recruited nationally and locally
- Compliance: assessments of acceptability and compliance during intervention

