#### 3.3.3 Peanut allergy diagnosis

It is vital to the study that the diagnosis is confirmed at the outset before group allocation, as determination of trial success depends on robust case definition. Therefore we will use the research gold-standard for diagnosis of active peanut allergy (DBPCFC) in all participants. The challenge is performed according to international consensus guidelines. This challenge will also identify the threshold for reactivity (minimum amount of peanut required to cause a reaction) that will be used during minimization for group allocation. At the outset we expect all participants to have active peanut allergy, therefore for safety reasons the challenge commences at a low dose (1-100mg). Only participants with a positive DBPCFC will be included in the study.

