## 6.2 Exclusion Criteria

1. Clinically significant chronic illness, except for eczema, rhinitis or asthma.

- 2. Suspected or diagnosed allergy to peanut protein in care provider or current household member.
- 3. Unwillingness or inability to comply with study requirements and procedures.

**7. Planned interventions:** (see figure 1) All subjects will undergo initial clinical characterization by history and allergy testing (skin prick tests), and DBPCFC with peanut at study enrollment. DBPCFC will confirm clinical peanut allergy and identify the amount of peanut required to cause a reaction (threshold level).

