#### 9.1.3 DBPCFC

On a day prior to the challenge, the study nurse will prepare the challenge doses in active (low dose recipes: 5, 50, and 100mg, 200mg) and placebo forms. A single peanut concentration mixture is used in each recipe for safety (i.e. each dose in the challenge is physically larger than the previous one so dose order cannot be accidentally reversed). All steps, including peanut weighing and labelling as active or placebo are double-checked with a colleague, who must be present throughout preparation. The order of each challenge is to be randomized independently by the laboratory research associate (independent of the clinical study) using an online minimization tool (www.randomizer.at). Record the randomization key in the challenge file. Each dose is administered in order separated by a **10-60m** interval and subjects are observed for 2 hours after

the last dose. If subjective symptoms of an allergic reaction occur (see table 1, section 9.1.6) they will be recorded and the apparent eliciting dose will be noted. If no objective signs appear, then the next highest challenge dose will be given in order. If subjective symptoms occur again with the next dose or are severe, then terminate the challenge and treat as appropriate. If objective signs occur at any stage then the eliciting dose is noted and the challenge is terminated, without further dose progression. A negative DBPCFC is followed by an open challenge of up to 12 peanuts. The outcome of the challenge (positive or negative-see below) and the apparent eliciting threshold dose will be recorded in the participant record.

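### Section 8.2 defines threshold as the amount tolerated while the rest of the protocol uses the eliciting dose; the fold increase differs several-fold between them and is undefined for first-step reactors

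*Protocol*

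**What the plan says.** The endpoint in protocol section 8.2 is "The fold increase and absolute increase in threshold (amount of peanut protein tolerated) for the active and control group members after intervention". Threshold there is an amount tolerated.

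Three other places use the word for the dose that provokes symptoms:

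- Section 3.3.3 refers to the "threshold for reactivity (minimum amount of peanut required to cause a reaction" and passes that value to the minimisation. Section 5.1 also lists the threshold dose among the minimisation factors.
- The opening of section 7 (printed directly after the exclusion criteria) says the entry challenge will "identify the amount of peanut required to cause a reaction (threshold level".
- Section 9.1.3 states what is written down at each challenge: "the apparent eliciting threshold dose will be recorded in the participant record".

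Section 9.1.3 gives the challenge doses as "low dose recipes: 5, 50, and 100mg, 200mg", and adds: "A negative DBPCFC is followed by an open challenge of up to 12 peanuts". Section 3.3.3 gives a different range, saying that "the challenge commences at a low dose (1-100mg".

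The protocol does not say whether the open challenge contributes to the threshold, or whether doses are single or cumulative.

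**The concern.** One word carries two meanings, in a minimisation factor and in an efficacy endpoint. On a coarse dose ladder the two meanings lie a full step apart, and the first step up is a factor of ten. The size of the reported fold increase therefore depends on which meaning the analyst adopts.

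The section 8.2 meaning also fails for one group when followed literally. A child who reacts at the first step has tolerated 0 mg, and a ratio to zero cannot be formed. If such children were left out, the summary would lose the most sensitive participants, whom section 3.3.6 deliberately keeps in the trial. At the other end, children who complete the challenge have only a lower bound. Treating that bound as a measured value would make their fold increase a function of baseline alone.

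**Working it through.** The protocol states no figure for this endpoint, so there is nothing to reproduce first.

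**Inputs.** Steps of 5, 50, 100 and 200 mg (section 9.1.3). Open challenge of at most 12 peanuts after a negative blinded challenge (section 9.1.3). 800 mg of protein corresponds to 5 to 7 peanuts (section 3.3.5, control group). A positive baseline challenge is required (sections 3.3.3 and 6.1). Planned pass rates are 64% active and 30% control (section 10). I assume the step doses are milligrams of protein and take the tolerated dose as the step below the eliciting dose.

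**Formulas.** Fold = post / baseline. Absolute increase = post − baseline.

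**1. The same child under both definitions.** Reacts at 50 mg before and at 200 mg after:

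- eliciting dose: 200/50 = 4-fold; 200 − 50 = +150 mg
- amount tolerated: 100/5 = 20-fold; 100 − 5 = +95 mg

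The fold results differ by 20/4 = 5 times, with no zero and no ceiling involved. Cumulative doses (5, 55, 155, 355 mg) do not remove the gap: 355/55 = 6.5-fold against 155/5 = 31-fold.

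**2. First-step reactor.** Reacts at 5 mg before and at 200 mg after:

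- eliciting dose: 200/5 = 40-fold; +195 mg
- amount tolerated: 100/0, undefined; absolute increase 100 − 0 = +100 mg, still defined

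A first step of 1 mg, as in section 3.3.3, would leave the same zero for any child who reacts to it.

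**3. Ceiling.** If only the blinded challenge counts, the highest amount tolerated is 200 mg. If the open challenge counts, the ceiling is 12 × 800/7 = 1371 mg to 12 × 800/5 = 1920 mg. For a child who completes everything, the fold is then fixed by baseline:

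| Baseline eliciting dose | Fold by eliciting dose, at least (1371–1920 mg) | Baseline tolerated | Fold by amount tolerated, at least (1371–1920 mg) |
|---|---|---|---|
| 5 mg | 274–384 | 0 mg | undefined |
| 50 mg | 27–38 | 5 mg | 274–384 |
| 100 mg | 14–19 | 50 mg | 27–38 |
| 200 mg | 7–10 | 100 mg | 14–19 |

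**4. How many reach the ceiling.** At the planned 64%, more than half of the active arm would pass. If all of them were placed above the top dose, the median post-treatment threshold in that arm would itself be only a lower bound.

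**The case against.** The strongest defence is that the endpoint defines its own quantity in its parenthesis, and that a reactivity threshold for diagnosis and minimisation can coexist with a tolerated amount as an outcome. The tolerated dose could then be read off as the step below the recorded eliciting dose. Conventions for zeros, ceilings and tests usually belong to the SAP, which is not at hand.

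Part of this stands. Missing conventions alone would be no finding. But an SAP would still inherit two meanings of one term, and the step-below rule still gives zero for first-step reactors. Nor is that rule always clear: section 9.1.3 notes an apparent eliciting dose at a first subjective symptom and yet lets the challenge go on.

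A reader might also infer more than the text supports:

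- *That the endpoint cannot be calculated.* The absolute increase remains defined for first-step reactors; only the fold fails.
- *That a child who passes the blinded challenge can have no eliciting dose.* The open challenge follows, and a child may react there.
- *That a child who tolerates 5 mg at baseline and 200 mg later shows 40-fold under one definition and only more than 4-fold under the other.* This sets a value against a lower bound, and 40 satisfies more than 4. The like-for-like contrast is 20-fold against 4-fold.
- *That switching to the eliciting dose, with every passer coded above the top dose, solves the problem.* At 64% passing it would make most active-arm increases lower bounds and discard the open-challenge information.

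**Conclusion.** The point holds for the definition and for the fold increase. The protocol uses threshold in two incompatible senses, and for an ordinary pair of challenge results the reported fold can differ five times (20 against 4). Under the section 8.2 wording the fold is undefined for first-step reactors, who are eligible but whose number is not given. The ceiling exists under either definition: the top blinded dose, or about 1371–1920 mg if the open challenge counts.

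These figures rest on the section 9.1.3 steps, single doses unless marked otherwise, and the protocol's own conversion between peanuts and milligrams. That conversion gives the range shown.

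This concerns one secondary endpoint. The primary comparison of pass proportions by Fisher's exact test does not use the threshold and is unaffected. The documents give no sign that a definition was chosen to suit results; the contradiction merely leaves the choice open in an open-label trial. It should be settled before the threshold data are analysed.

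**What to change.** 1. Use one definition of threshold, in the same words, for the minimisation factor and for the section 8.2 endpoint. State whether doses are single or cumulative.
2. State whether the open challenge counts towards the threshold.
3. Make the between-arm comparison a rank test on the ordered dose step, or an interval-censored regression of log dose adjusted for baseline step. Put first-step reactors in the lowest category and completers in the highest, so that no child is dropped for want of a computable ratio. With the tolerated dose taken as the step below the eliciting dose, both definitions order the steps alike, so the rank comparison does not depend on the choice.
4. Report fold and absolute increases descriptively only. Mark values at the ceiling as lower bounds, including a median that falls there, and compute no fold from a zero baseline; give the number of such children instead.
5. Reconcile the challenge ranges in section 3.3.3 (1–100 mg) and section 9.1.3 (5–200 mg), since the dose categories depend on them. Which is right is for the investigators to say.

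The cost is a change of wording and a slightly less intuitive summary of one secondary endpoint. The primary analysis and the sample size do not change.

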#### 9. Assessment and follow up:

**9.1 Assessment of efficacy/effectiveness:** Determination of peanut allergy at various assessment points will be achieved by double blind placebo controlled peanut challenges

#### 9.1.1 Challenge timing

All participants will undergo a DBPCFC at enrolment (we expect the majority to react during this) After six-seven months the active and control group subjects undergo a second DBPCFC. The control group will then undergo immunotherapy, after six-seven months they also undergo a final DBPCFC.

#### 9.1.2 Perform clinical assessment

All subjects will be assessed to determine their suitability for a challenge. A participant's eligibility for a challenge is guided by the following criteria:

The subject has had no acute exacerbation of allergic signs or symptoms within the last week, has not received short-acting beta-2 agonists for 12 hours, long-acting beta-2 agonists for 24 hours, short-acting antihistamines in the last 48 hours, or long-acting antihistamines in the last 7 days. The subject has no concurrent illness. Prior to conducting challenges, do the following: Ensure that both oxygen and suction are in working order. Ensure that all steps of the anaphylaxis protocol are in place and that all emergency drugs are readily available. Record baseline observations. One of the following challenge methods will be chosen depending on group allocation and position in the trial (see flow chart figure 1)

#### 9.1.3 DBPCFC

On a day prior to the challenge, the study nurse will prepare the challenge doses in active (low dose recipes: 5, 50, and 100mg, 200mg) and placebo forms. A single peanut concentration mixture is used in each recipe for safety (i.e. each dose in the challenge is physically larger than the previous one so dose order cannot be accidentally reversed). All steps, including peanut weighing and labelling as active or placebo are double-checked with a colleague, who must be present throughout preparation. The order of each challenge is to be randomized independently by the laboratory research associate (independent of the clinical study) using an online minimization tool (www.randomizer.at). Record the randomization key in the challenge file. Each dose is administered in order separated by a **10-60m** interval and subjects are observed for 2 hours after

the last dose. If subjective symptoms of an allergic reaction occur (see table 1, section 9.1.6) they will be recorded and the apparent eliciting dose will be noted. If no objective signs appear, then the next highest challenge dose will be given in order. If subjective symptoms occur again with the next dose or are severe, then terminate the challenge and treat as appropriate. If objective signs occur at any stage then the eliciting dose is noted and the challenge is terminated, without further dose progression. A negative DBPCFC is followed by an open challenge of up to 12 peanuts. The outcome of the challenge (positive or negative-see below) and the apparent eliciting threshold dose will be recorded in the participant record.

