#### 3.3.4 Group allocation

Within an individual various factors including severity of allergy (from history and challenge), age, presence of asthma, and other active allergies, are known to influence reactivity and thus may influence the successful response to immunotherapy. Random group allocation may result in an imbalance of these factors between the active and control groups, leading to bias. To account for this, subjects will be allocated using minimization, with a random element using a weighting probability of 0.8.

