#### Control group

We have added a control group. There are no data on resolution in severe peanut allergy. The allergy may resolve in up to 20% of mildly peanut allergic children. This is thought to happen slowly over a number of years, rather than the relatively short period of our study. The control group will undergo peanut avoidance for five months (current practice) during which time they are on the 'waiting list' before receiving active intervention. A recent study demonstrates precedent of using a waiting list control group: 45 children with egg and cow's milk allergy were randomised to waiting list control or oral immunotherapy. After 18-24 months all control group subjects had a positive food challenge, demonstrating persistence of their allergy. Subjects randomized to the control group will receive the current best management (peanut avoidance management plan) for six-seven months [in pilot duration was 58-210d (median 143d, mean 140d; about 5 months) n=12;]. This is provided using verbal and written information provision and training in the use of emergency medication and provision of an emergency treatment plan. In an ideal world, we would administer a placebo to participants in our control arm and this was considered in great detail during development work. The main reason for not including a placebo is the impossibility of being able to adequately blind an active or placebo snack. Importantly, in our open design pilot study 70% of children had reactions immediately after taking an active dose, meaning participating families (and the investigators) would quickly work out which arm of the study they were on. After development work, we also concluded that it was not possible to adequately mask larger doses of peanut protein in a snack size acceptable for a child to eat every day (800mg is the equivalent of 5-7 peanuts). An alternative would be to provide a peanut-flavored placebo snack, but it would be unethical to leave families on either arm in doubt as to whether oral tolerance had been induced or not. Families who falsely assume they are on the active treatment arm may relax their allergen avoidance practice, thereby putting their child at increased risk of a reaction. We feel that a placebo arm would also hamper recruitment and compliance. The obvious disadvantage of not including a placebo snack is that subjects will know which study arm they are assigned to. This is offset by the fact that the primary outcome (peanut allergy) will be diagnosed on the basis of an objective measure: double blind, placebo-controlled food challenge (DBPCFC), the gold-standard for food allergy diagnosis in research. On peanut challenge, neither the investigator, the nurse, nor the participant will know whether the participant's dose is peanut or placebo, so it will be impossible for the outcome of the challenge to be influenced by that knowledge.

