**17. Justification of support required:** This is a clinical trial with frequent high-intensity clinical interventions which requires close clinical supervision by a doctor and nurse at all times, for safe conduct. [name] (Clinical research associate; 1.0 WTE) will supervise peanut challenges and immunotherapy doses; she will work towards a PhD within this project, examining clinical and immunological features of oral immunotherapy. [name] (Grade G nurse; 1.0 WTE) will prepare and perform oral challenges and immunotherapy with [name]. [name] is a post doctoral scientist (research associate 7; 1.0 WTE) and will develop and perform the immunological assays with [name], prepare updosing and double-check challenge preparation. [name] is also responsible for training and supervision. All will contribute to manuscript preparation. [name] (University Lecturer) is trial statistician and will prepare statistical reports and perform statistical analysis.

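### The peanut/placebo order of each challenge is set by a minimization tool with no stated settings, so the order may be guessable above chance by a team that knows the arm

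*Protocol*

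**What the plan says.** Section 9.1.3 (DBPCFC) says that the order of each challenge is "randomized independently by the laboratory research associate (independent of the clinical study) using an online minimization tool". It then instructs: "Record the randomization key in the challenge file". It gives no balancing factors, no random element, and no rule on who may see the key or when.

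The only random element in the protocol is in section 3.3.4, for allocation to trial arm: "subjects will be allocated using minimization, with a random element using a weighting probability of 0.8".

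Section 3.3.5 (Control group) accepts that "subjects will know which study arm they are assigned to" and offsets this with the blinded challenge. It says that "neither the investigator, the nurse, nor the participant will know whether the participant's dose is peanut or placebo", and concludes "so it will be impossible for the outcome of the challenge to be influenced by that knowledge".

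Section 3.3.3 adds: "Only participants with a positive DBPCFC will be included in the study". Under section 9.1.4 a challenge is positive on one objective sign or two subjective symptoms; the latter include oral itching, nausea and mild abdominal pain. Section 17 describes one clinical research associate and one nurse who run the challenges. It also describes a post-doctoral research associate whose tasks include to "prepare updosing and double-check challenge preparation".

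**The concern.** Minimization picks the next assignment to offset the imbalance left by earlier ones. That helps when children are allocated to arms and prognostic factors should be balanced. It has no evident use for the order of two challenge sessions within one child: every child receives both peanut and placebo, the result is read within the child, and no analysis in section 11 uses order.

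The price is dependence on the past. Each included child must have reacted to peanut at enrolment, and the threshold dose feeds group allocation, so those challenges have to be attributed to peanut or placebo before the second challenges are judged. This gives a small single-centre team a history from which to guess.

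What is at stake is the primary outcome's main safeguard. Whoever judges subjective symptoms may know the arm. If that person can also guess which session contains peanut, symptoms could be probed for or discounted differently by arm. Concealed labels would not close this route, because the guess comes from past orders.

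**Working it through.** **The plan's own figure.** The protocol gives no figure for predictability. Its power statement in section 10 (Fisher's exact test, 64% vs 30%, 49 per group, two-sided 0.05, 90% power) reproduces: exact power is 0.906, and 98/0.95 rounds up to 104 recruited. This point does not touch it.

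**Inputs.**
- From the protocol: 104 enrolment challenges; 98 second challenges (2 × 49); planning pass rates of 64% and 30%.
- Assumed: challenges are ordered one after another; p is the probability that the tool assigns the order used less often so far; ties are broken 50:50. The protocol gives no p for challenge order, so 0.5 (simple randomisation), 0.8 (borrowed from group allocation) and 1.0 (no random element) are shown.

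**All past orders known, overall balancing only.** The guesser always names the order used less often. With r = p/(1 − p), the long-run share of correct guesses is 1/2 + (r − 1)/(4r).
- p = 0.5: r = 1, giving 0.50.
- p = 0.8: r = 4, giving 1/2 + 3/16 = 0.6875. Simulation gives 0.68 to 0.69.
- p = 1.0: steps alternate between a tie (50%) and certainty (100%), so (0.5 + 1.0)/2 = 0.75. Simulation gives 0.75.

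**Only some second challenges decoded.** A child who reacts in neither session has a negative challenge whatever the order, so nothing need be revealed. At the planning rates that is (0.64 + 0.30)/2 = 0.47 of second challenges, leaving 0.53 that react. Simulated with all 104 enrolment orders known and 53% of the 98 second-challenge orders decoded, the correct-guess rate at the second challenge is:
- running-tally rule: about 54%, at p = 0.8 and at p = 1.0. The undecoded orders make the tally drift away from the true imbalance.
- rule that names the opposite of the last known order: about 56-63%, the upper end being the case with no random element.

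**If balancing factors were used (also not stated).** At p = 0.8 with six binary factors, a guesser who knows everything scores 78%. One who knows only overall totals scores 63-64% with one or six factors. With no random element, six factors and full knowledge, the rate is 95%. These show how widely the answer depends on settings; they are not expected values.

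| Situation (overall balancing) | Correct guesses |
|---|---|
| Simple randomisation, whatever is known | 50% |
| Only reacting second challenges decoded | about 54-63% |
| 0.8 weighting, all past orders known | about 69% |
| No random element, all past orders known | 75% |

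**The case against.** The strongest reply is that predictability is inferred. Section 9.1.3 says that the order is randomized and gives the task to someone described as independent of the clinical study. The tool may have been set to simple randomisation, in which case the guess rate is 50%. The protocol does not say that the team is told past orders, and a child who reacts in neither session need not be decoded. All of this stands. It is why the result is a range, and why 69% and 75% are ceilings under overall balancing. Even the assumption that every enrolment order is known favours the guesser: section 9.1.1 expects most, not all, children to react at enrolment, and those who do not react need not be decoded either.

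The reply also notes that harm requires staff to keep a tally, act on an uncertain guess and move a borderline result, and that objective signs decide some challenges. That stands too: no change in pass rates can be derived from the protocol.

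A third reply is that concealed past orders or a sealed key would also help. They would, but simple randomisation removes the dependence on past orders altogether.

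A reader might also infer that the list-holder is plainly not independent, given the tasks in section 17. The protocol does not go that far. Section 17 uses a different job title and does not claim to list all staff. The conflict exists only if the laboratory research associate of section 9.1.3 and the post-doctoral research associate of section 17 are the same person.

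None of this supplies a reason to balance the order. Nor is this a detail left to a statistical analysis plan: the protocol itself names the method.

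**Conclusion.** The point holds in a conditional form. The protocol names a method for challenge order that makes each order depend on earlier ones, states no random element for it, and gains nothing for any stated analysis. Depending on settings and access that are not given, the correct-guess rate under overall balancing runs from 50% through about 54-63% to about 69-75%. The upper figures need every past order to be known.

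A reader might conclude that the next order can be guessed well above chance, or that the primary comparison is biased. The protocol supports neither as fact. What it supports is that the assurance in section 3.3.5, that influence on the challenge outcome is impossible, is stronger than the method in section 9.1.3 can guarantee. The arms are open and two subjective symptoms suffice for a positive result, so the change is worth making. The sample size and power are unaffected.

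**What to change.** In section 9.1.3, replace the minimization tool for challenge order with simple (unrestricted) 1:1 computer randomisation for each challenge, with no balancing across children, arms or a child's earlier challenges. Keep minimization for group allocation only. The guess rate from past orders is then 50%, whatever the team has learned.

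In the same edit, state that the order is generated by someone who prepares no doses. If the laboratory research associate is the post-doctoral research associate of section 17, reconcile the two descriptions.

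The cost is a sentence or two in section 9.1.3 and a different method of generating the order. The small downside is that peanut-first and placebo-first challenges may differ in number by chance, which no stated analysis depends on.
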